25.2.2.2 Analysis

Summary statistics of the number and percentage who experienced the outcome will be presented by trial arm, country and time-period. The denominator for the percentage calculation will be the number of live births recorded in the facility in the time period.

Outcome rates over time will be presented in a line graph, split by intervention vs control, with prerandomisation, transition and post-randomisation phases marked. Time will be anchored around date of allocation to the transition phase for each facility.

The primary analysis will use a mixed effects logistic regression models with robust standard errors. A small sample correction will not be used as there are over 40 clusters [8] The model will incorporate a constrained baseline analysis [9], where both pre-randomisation and post-randomisation time points are included as outcomes, but with the treatment effect assumed to be zero in the pre-randomisation phase. This will be implemented using two binary covariates, one indicating period (0= pre-randomisation, 1=post-randomisation), and one indicating exposure to the intervention (taking the value 0 for all clusters in the pre-randomisation period, and control clusters in the post-randomisation period, and the value 1 for the intervention clusters in the post-randomisation period). Facility and facility by period will be included as random effects, with country, and the categorical minimisation factor facility size included as covariates. The second minimisation factor (proportion of births with the composite primary outcome) is not included as proportion of births is already in the model as the outcome variable. Relative risk and risk differences will be derived using marginal standardisation, as in Kirkwood et al [10]. Under this approach, the mean risk under the control condition and intervention condition is obtained. The risk ratio is then derived using the mean risk in intervention condition and by the mean risk in the control condition, with the calculation being performed on the log scale. The risk difference is derived as the mean risk in intervention condition minus the mean risk in the control condition. We will use the unconditional standard errors to obtain the confidence interval, as this allows for correlation amongst the observations. Point estimates, 95% confidence intervals and exact p-Values will be reported. Estimation of the relative risks and risk differences, and their standard errors and confidence intervals

will be carried out using the 'margins' command in Stata, as this method has not been implemented in SAS.

If the full mixed effects model fails to converge, we will follow the sequence of analyses:

- 1. Remove the random facility by period effect and fit a mixed effects model with random effect for facility only.
- 2. If this model also fails to converge, we will perform a cluster level analysis weighted by cluster size, calculating a cluster-level summary statistic for the pre-randomisation period and post randomisation period separately.

Queries will be raised where daily reporting of aggregate data appear to be inconsistent within care areas (e.g. a care area has reported births on one day but not the next) or where days with reporting are missing within the week.

Covariate data (country and facility size) will be complete. Country is known for each cluster and facility size is based on the number of births per cluster per week in the pre-randomisation phase.

Additional analysis

Subgroup analyses will be carried out by including a treatment group by subgroup interaction parameter in the regression model and reporting adjusted treatment effects with 95% confidence intervals. Treatment effects will be compared between subgroups using ratios of ratios using post-estimation commands. Results of subgroup analyses will be interpreted cautiously. Subgroups will include country, facility size and month of post intervention roll-out period.

Intracluster correlation coefficients and cluster autocorrelation

Estimates of ICC and CAC will be calculated on the proportion scale by fitting multilevel linear models to the binary data. Within-period ICCs for the pre-randomisation and post-randomisation periods, and between period CAC will be reported.

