7 STUDY DESIGN

The study is a multi-country, parallel cluster randomised trial with a baseline control phase. There is an integrated implementation evaluation and health economic evaluation. The trial will include 60 clusters, each of which is a health facility (30 in Malawi and 30 in Uganda).

During the first six months each cluster will continue with their current practices and data will be collected to establish weekly rates of maternal infection and mortality experienced which will act as baseline period.

After the baseline period, the clusters will be randomly allocated in a 1:1 ratio to the APT-Sepsis programme or current practice with passive guideline dissemination, using a minimisation algorithm. There will be a three-month transition period during which the APT-Sepsis programme will be introduced to the clusters randomised to the intervention. Data collected during the three-month transition will not contribute to the analysis.

The intervention is delivered at a health facility level and targets the health care providers and systems within the facility. The intervention seeks to change the behaviours of health care providers to improve adherence to WHO guidelines and best practice in infection prevention and management, and detection and management of maternal sepsis.

The post-randomisation phase (including the transition period) will be for a period of twelve months. A detailed understanding of how the intervention is operationalised in practice, will be assessed from a behaviour change perspective.

In the final months of the study, we will complete the data analysis and work with the PPI team and Maternal Sepsis Support groups to disseminate the information about findings.

7.1 **Blinding**

This is an open label study with no blinding requirements. All researchers and participants will know which intervention the cluster has been randomised to the APT-Sepsis programme.

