11.3 Removal of participants from intervention or follow-up

At present there are no planned instances where a participant or facility would be removed from the intervention or post intervention roll out period. Facilities that drop out during the baseline period will not be included in the final analysis.

12 Method of assignment to intervention

A minimisation system was configured by an independent statistician at LCTC. Health facilities were allocated to treatment arms using a minimisation algorithm, to ensure balance of important factors between facilities allocated to the intervention and control groups. The minimisation factors within each country were

- 1. number of births per cluster per week: three categories: cut points 70.8 and 118.5 (Malawi), 60.5 and 83.9 (Uganda).
- 2. proportion of births with the composite primary outcome (infection related maternal mortality, infection related maternal near-miss and severe infection related morbidity see Section 15.1): two categories: cut points 1.96 (Malawi), 3.19 (Uganda).

These were be measured at each facility within the baseline period. The cut points for the minimisation factors were determined separately for each country. Weekly average births were assigned into 3 categories using the 33rd and 67th percentile of the observed values within up to the first four months of the baseline periods. Start dates were staggered, therefore, we had between two and four months of baseline data for each facility to determine cut-points. Proportion of births with the composite primary outcome were assigned into 2 categories using the median as a cut-off point. Facilities were allocated during the fifth month of their baseline period, using their baseline data up to this point (at least four months for each facility).

The minimisation algorithm will calculate the allocation which will minimise imbalance over all minimisation factors. A random element of 90% will be incorporated to reduce predictability of allocation, with facilities allocated to the group which minimises imbalance with probability 0.9, or to the other group with probability 0.1. If both allocations would result in equal imbalance, the allocation will be determined completely at random [1].

13 Schedule of assessments

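### Country and facility-size subgroup intervals inherit a waiver justified by having over 40 clusters, although they rest on about 30 and 20 facilities and come out modestly too narrow

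*SAP*

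**What the plan says.** SAP 25.2.2.2 sets the main model: "The primary analysis will use a mixed effects logistic regression models with robust standard errors". The next sentence settles the small-sample question: "A small sample correction will not be used as there are over 40 clusters", with a cited systematic review of simulation studies in support. The model structure is: "Facility and facility by period will be included as random effects, with country, and the categorical minimisation factor facility size included as covariates".

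Under Additional analysis in the same section, the SAP says: "Subgroup analyses will be carried out by including a treatment group by subgroup interaction parameter in the regression model". It promises adjusted effects with 95% intervals and compares subgroups by ratios of ratios. "Subgroups will include country, facility size and month of post intervention roll-out period". No variance estimator, reference distribution or degrees of freedom is given for these analyses. The only qualification is: "Results of subgroup analyses will be interpreted cautiously".

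The cluster counts come from elsewhere. Protocol section 7 gives "30 in Malawi and 30 in Uganda", allocated 1:1. SAP section 12 forms the size categories within each country: "Weekly average births were assigned into 3 categories using the 33rd and 67th percentile". SAP 9.1 aims to open 64 facilities, which includes two spare per country.

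**The concern.** The only reason given for omitting a correction is that there are more than 40 clusters. Country and facility size are cluster-level factors, so they divide the clusters, and no country or size category reaches 40. A programmer following the SAP would still use the uncorrected robust error with a normal quantile, because that is the only rule given.

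A sandwich variance built from few clusters is biased downwards and is itself variable. A normal quantile allows for neither, so the intervals are too short.

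Subgroup effects are a stated secondary objective (Protocol 6.3.2, SAP 8), and findings are to be shared with the ministries of health in Malawi and Uganda (Protocol 27.3). Country-specific intervals are therefore likely to be read on their own. SAP 25.2.3 exempts secondary outcomes from testing. The subgroup text has no such exemption, and SAP 25.2.1 sets two-sided 5% tests wherever a test applies.

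**Working it through.** The plan gives no figure for subgroup coverage or precision, so there is none to reproduce.

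**Cluster counts.** Country: 60/2 = 30, about 15 intervention. Size category: 60/3 = 20, about 10 intervention. If all 64 opened facilities were randomised: 64/2 = 32 and 64/3 ≈ 21. All are below 40. Month of roll-out does not divide the facilities.

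**Inputs from the documents.** ICC 0.021 (SAP 16.1); CAC 0.97, with 0.9 as the lower sensitivity limit (SAP 16.2); 6 months of baseline and 9 months after transition (SAP 9.1), taken as 26 and 39 weeks; constrained baseline with facility and facility-by-period random effects (SAP 25.2.2.2).

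**Assumed inputs.** Event rate 2.6%. This is close to the midpoint of the two cut points in SAP 12, read as percentages: (1.96 + 3.19)/2 = 2.58. Weekly births by size category: 50/95/160 (Malawi) and 45/72/110 (Uganda), consistent with the SAP 12 cut points.

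**Simulation of the single model.** There were 60 facilities, 10 per country-by-size cell (5 per arm), with 2,700 datasets per CAC. The model was fitted to cluster-period empirical logits, an approximation to the logistic mixed model. The uncorrected interval uses the cluster sandwich with factor M/(M−1) and z = 1.96. The corrected interval uses a Kauermann-Carroll-type sandwich with t on 58, 28 or 18 degrees of freedom. The SAP does not say whether period also interacts with subgroup, so both readings were fitted. Monte Carlo standard error is about 0.3-0.5 points.

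| Effect | Period effect | Uncorrected, CAC 0.97 | Uncorrected, CAC 0.90 | Corrected (0.97 / 0.90) |
|---|---|---|---|---|
| Overall | common | 93.6% | 93.6% | 94.5 / 94.3% |
| Country | common | 92.9% | 93.5% | 94.6 / 95.0% |
| Country | by subgroup | 92.3% | 93.0% | 94.2 / 94.9% |
| Size | common | 91.6% | 92.3% | 94.5 / 94.9% |
| Size | by subgroup | 91.6% | 92.0% | 94.5 / 94.9% |

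**Check by formula.** At CAC 0.97 with a common period effect, the mean robust error divided by the empirical SD averaged (0.948 + 0.948 + 0.981)/3 = 0.959 for country and (0.925 + 0.937 + 0.949)/3 = 0.937 for size. Treating the statistic as t:
- country: P(|t28| < 1.96 × 0.959) = 92.9%
- size: P(|t18| < 1.96 × 0.937) = 91.7%

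Both agree with the table.

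**Interactions.** Two simpler simulations of one 60-facility model, with known variance components and the normal quantile, gave rejection rates under no effect of:
- country interaction: 5.9-6.8%
- size interaction: 6.8-7.9%
- country effects: 6.2-7.2%
- size effects: 7.1-8.1%
- overall effect: 5.1-5.5%

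Known variance components may make these slightly optimistic.

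**Width after correction.** The t quantile alone adds 2.048/1.960 = 1.045 (28 df) or 2.101/1.960 = 1.072 (18 df). With the variance correction, the total ratio was 1.07-1.08 for country and 1.11-1.13 for size.

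**The case against.** The waiver sentence directly follows the description of the primary analysis and is not stated for subgroups. Carrying it over is an inference. That stands, but the subgroup text adds a term to that same regression model and offers no other rule, so the inference is what an analyst would act on.

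The subgroup effects come from one model fitted to all 60 facilities. With a common period effect, all 30 controls inform the change over time behind each subgroup estimate. It would therefore be wrong to say that a subgroup's robust variance is built only from its own facilities. This also stands, and it limits the size of the problem. It does not remove it, because only about 15 or 10 intervention facilities carry each estimate, and the common-period rows of the table still under-cover.

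A reader might treat each subgroup as a separate trial of 30 or 20 facilities. Separate facility-level fits do give false-positive rates of about 8.0-8.6% and 9.3-9.8%, but the SAP does not specify separate fits, so those rates do not describe its analysis.

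A reader might also infer that the primary analysis is unsound. The documents do not support that: the overall comparison meets the SAP's stated condition, a reference is cited for the choice, and the checks show coverage of 93.6% or rejection of 5.1-5.5%. For country, the shortfall is only slightly worse than for the overall effect.

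Finally, both documents promise cautious interpretation of subgroups. That lowers the stakes, but it does not make an interval labelled 95% cover 95%.

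**Conclusion.** The point holds at a modest size. As written, the country and facility-size subgroup intervals take uncorrected robust errors under a waiver whose condition those subgroups do not meet. Nominal 95% intervals cover about 92-94% for country and 91.5-92.5% for size. Interaction tests reject at about 6-7% and 7-8% instead of 5%. Facility size is the clearer case.

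The direction was the same in every simulation. The exact figures rest on the assumed 2.6% event rate and cluster sizes, and on approximations to the logistic mixed model. They were not run through the SAP's marginal standardisation step. The content of the SAP's cited review was not available. The primary conclusion and the month-of-roll-out subgroup are not affected.

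**What to change.** In SAP 25.2.2.2:

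1. State that the waiver applies to the overall comparison only.
2. For country and facility-size effects and their ratios of ratios, name a small-sample corrected robust variance and use t quantiles.
3. State the degrees of freedom. For a subgroup effect, use facilities minus 2: 30 − 2 = 28 (country) and 20 − 2 = 18 (size). For an interaction, use facilities in the compared subgroups minus the number of arm-by-subgroup cells: 60 − 4 = 56 (country) and 40 − 4 = 36 (a pair of size categories). A rule that counts facilities within one subgroup only would be undefined for an interaction. Replace these counts with the numbers actually randomised.
4. State whether period-by-subgroup terms are included.

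The cost is some post-estimation programming and intervals wider by about 7-8% (country) and 11-13% (size). No new data or design change is needed. The correction was checked for subgroup effects. Its calibration for the ratios of ratios was not reported, so a short simulation before the wording is fixed would be sensible.

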17.2 Method of Randomisation

17.2.1 Allocation Sequence Generation

Health facilities will be allocated to groups using a minimisation algorithm, to ensure balance of important factors between facilities allocated to the intervention and control groups. The minimisation factors will be:

Allocation will be stratified by country. The minimisation factors within each country will be:

- 1. number of births per cluster per week
- 2. proportion of births with the composite primary outcome

These will be measured at each facility within the baseline period. The cut points for the factors will be determined separately for each country using quantiles of the observed values within up to the first four months of the baseline periods: start dates will be staggered, we will have between two and four months of

baseline data for each facility to determine cut-points. Facilities will be allocated no earlier than the fifth month of their baseline period, using their baseline data up to this point (at least four months for each facility).

The algorithm will be implemented using the minimisation option in the LCTC generic randomisation system, which has been fully tested and validated. The algorithm will calculate the allocation which will minimise imbalance over all minimisation factors. A random element of 90% will be incorporated to reduce predictability of allocation, with facilities allocated to the group which minimises imbalance with probability 0.9, or to the other group with probability 0.1. If both allocations would result in equal imbalance, the allocation will be determined completely at random.

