16.2 Original sample size calculation

To this end, we have assumed an ICC of 0.03 but considered sensitivity across the range 0.001 to 0.05. We have assumed a CAC of 0.97 but considered sensitivity across the range 0.9 to 1.0. Each health facility will have a minimum of 1,500 births each year, so each health facility will contribute 2,875 (=1,500*23/12) births to the analysis (750 during the baseline phase and 2,125 post randomisation). Assuming 60 health facilities, the total sample size will be 172,500. Using methods to calculate the sample size in a parallel CRT with a baseline period previously described [6, 8] this will give over 95% power (at 5% significance) to detect a 25% relative reduction in the composite primary outcome from 3% to 2.25% after adjusting for clustering through the ICC and CAC for our base case scenario. The ICC and CAC ranges were considered through sensitivity analysis, and the study has at least 80% power in most likely scenarios. Our calculations have not allowed for varying cluster size, but our allocation process will balance on cluster size to ensure total cluster sizes are similar across the two arms of the study (see Section 12).

To allow for the possibility of health facilities dropping out, we will recruit an extra two facilities per country. It is anticipated that drop out is most likely to happen during the baseline period, in which case, these facilities will not be randomised or included in the final analysis.

17 Study Framework

The overall objectives of the primary and secondary outcomes is to test superiority of the APT-Sepsis programme compared to usual care with passive guideline dissemination

18 Timing and Objectives of Analyses

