25.2 Final Analysis

25.2.1 Levels of significance and multiplicity

All applicable statistical tests will be two-sided and will be performed using a 5% significance level; confidence intervals presented will be 95%.

There will be no adjustment for multiplicity. However, results from secondary outcomes will be considered as exploratory and results will be interpreted with caution.

Analyses will be conducted with all clusters assigned to the group they were assigned at randomisation. All observations from randomised facilities (excluding observations from the transition phase) will be included in the analysis.

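### One period effect shared by Malawi and Uganda widens the primary confidence interval if their trends differ, and biases the country subgroup comparison

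*SAP*

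**What the plan says.** SAP 25.2.2.2 sets out a mixed logistic model with a constrained baseline and robust standard errors. It has one binary indicator for period and one for exposure to the intervention. Beyond these, "Facility and facility by period will be included as random effects, with country, and the categorical minimisation factor facility size included as covariates". Protocol 17.4 names the same covariates. Neither document has a country-by-period or size-by-period term. The only interactions are treatment-by-subgroup terms, under Additional analysis in SAP 25.2.2.2, where country and facility size are both listed as subgroups.

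On allocation, protocol 17.2.1 says "Allocation will be stratified by country", with minimisation inside each country. SAP section 12 adds that "The cut points for the minimisation factors were determined separately for each country".

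**The concern.** Each facility serves largely as its own control, so the treatment effect is identified mainly by change from baseline to follow-up. A country or size effect that is the same in both periods does little to that change. What could matter is a change over time that differs by country, and the model allows none: all control facilities share one period effect.

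Two things are at stake.

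- **Overall effect.** With arms balanced within country, a trend difference falls equally on both arms and does not move the estimate. The model nevertheless reads it as unexplained facility-by-period variation, so the reported standard error exceeds the true sampling error.
- **Country subgroup.** Once a treatment-by-country term is added to the same model, that term is the only place where a country-specific change can go.

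Differing trends are plausible. A baseline of about six months and a nine-month follow-up do not span the same calendar months, and protocol 10.1 and 14.2 expect supplies and local policy to vary during the study.

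**Working it through.** **Inputs.** ICC 0.021 (SAP 16.1). CAC 0.97 (SAP 16.2; not restated in the revision). 60 facilities, 15 per arm in each country (protocol 6.2). Minimum volume of 1,500 births a year gives 750 births in 6 months and 1,125 in 9. As an alternative I assume 80 births a week, a value between the SAP section 12 cut points, giving 2,080 and 3,120. Mean risk is 2.625%, so s² = 0.02625 × 0.97375 = 0.02556. Tests are two-sided at 5%. *Assumed, not in the documents:* the country trend difference D, and a between-facility variance of 0.6 on the log-odds scale.

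**1. The plan's power figure.** SAP 16.2 states over 95% power to "detect a 25% relative reduction in the composite primary outcome from 3% to 2.25", with "750 during the baseline phase and 2,125 post randomisation" births per facility. In units of s², Vjj = (1 − ICC)/mj + ICC, V12 = ICC × CAC, residual R = V22 − V12²/V11, and SE = √(2/30 × s² × R).

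- Original inputs: R = 0.030456 − 0.0291²/0.031293 = 0.003396; SE = 0.00241; power = Φ(0.0075/0.00241 − 1.96), about 88%.
- Other readings of the inputs give 95.8% (2,875 births in each period), 98.3% (CAC 0.995) or 98.7% (CAC applied to monthly periods). The period length behind the CAC is not stated, so I do not call the figure wrong. It does not bear on this point.
- Revised design at minimum volume: R = 0.021870 − 0.02037²/0.022305 = 0.003267; SE = 0.00236; power 88.9%, consistent with the stated 80% or more.

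**2. How much of a time-constant effect remains.** The weight on the facility's own baseline is b = V12/V11.

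- Minimum volume: 0.02037/0.022305 = 0.913.
- 80 births a week: 0.02037/(0.979/2,080 + 0.021) = 0.949.

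So 5–9% of a country or size main effect remains (about 2–15% for CAC between 0.9 and 0.995). In simulation with equal trends, the main effects left the mean robust SE almost unchanged: 0.0706, against 0.0708 with no covariates.

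**3. Width of the primary interval.** With half the facilities in each country, an omitted trend difference D adds D²/4 to R. The reported SE is then multiplied by √(1 + D²/(4R)). On the log-odds scale at 80 births a week, sampling variances are 1/(2,080 × 0.02556) = 0.0188 and 1/(3,120 × 0.02556) = 0.0125. Then R = 0.6125 − 0.582²/0.6188 = 0.0652 and SE = √(2/30 × 0.0652) = 0.066.

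| D (log-odds) | Formula | Simulation A: SE without / with term | Simulation B: SE without / with term |
|---|---|---|---|
| 0 | 0% | 0.0789 / 0.0782 (+1%) | 0.0706 / 0.0700 (+1%) |
| 0.2 | √(1 + 0.01/0.0652): +7% | 0.0836 / 0.0793 (+5%) | 0.0750 / 0.0698 (+7%) |
| 0.4 | √(1 + 0.04/0.0652): +27% | 0.0933 / 0.0788 (+18%) | 0.0881 / 0.0702 (+25%; D = 0.405) |

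The term is country-by-period. A: 800 trials per setting, mixed model on facility-period log-odds. B: 300 trials per setting, the SAP's logistic mixed model. Both use robust SEs and allocation balanced within country and size. In B the SAP model's true sampling SD was 0.0684 at D = 0.2 and 0.0741 at 0.405, below the reported SEs. Coverage was 96% and 99%, and bias at most 0.007.

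**4. Power at the planned effect.** In B, power was 96% without the term and 98% with it at D = 0.405. At an extreme D of 0.693 it was 82% and 98%. On the risk scale at minimum volume with a trend difference of 1 percentage point, the reported SE is 14% larger. Power is Φ((0.0075 − 1.96 × 0.00236 × 1.14)/0.00236), about 83%, with the true SD unchanged. Treating the inflated SE as the true SD gives 79.6%.

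**5. Country subgroup.** Without the term, the treatment-by-country estimate absorbs a fraction 1/(1 + q) of D, where q = (1 − b)²V11/(2R).

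- Minimum volume: q = 0.0868² × 0.022305/(2 × 0.003267) = 0.026; fraction 0.97.
- Log-odds scale: b = 0.582/0.6188 = 0.9405; q = 0.0595² × 0.6188/(2 × 0.0652) = 0.017; fraction 0.98.

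At D = 0.2 the false interaction is 0.98 × 0.2 = 0.197. Its SE is about √(2 × 0.0652/15) = 0.093, so its interval excludes the null with probability about Φ(0.197/0.093 − 1.96) = 56%. Simulation gave 54–56%, against 5–6% with the term.

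**The case against.** The strongest reply is that adjustment for country and size is pre-specified, the primary estimate is unbiased, and the interval errs on the safe side. On this view, interactions with period are an efficiency preference. For the overall effect that stands. Several stronger readings are tempting, and the documents do not support them:

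- *Country and size cancel, so the stratification is ignored.* Both factors are in the model, and 5–9% of their effect remains.
- *The countries' trends do differ.* The cut points for the outcome proportion (1.96 in Malawi, 3.19 in Uganda) show a difference in level. No document reports a trend.
- *The trial loses its power.* At the planned effect it stays above 80% over the range considered. Planning also tested CAC down to 0.9, and an unmodelled trend acts like a lower CAC.

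A second reply is that larger models with uncorrected robust SEs may under-cover. Simulation B gave 91–94% for them, but the SAP's own model gave 93.0% with equal trends, against 92.3% with country-by-period. Another simulation gave 94–95% with the term. This is a reason to check the small-sample choice, and a weak one for leaving the term out.

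Third, minimisation has a 0.9 random element, so balance within country need not be exact. If the intervention arm had 16 facilities from one country and 14 from the other, and the control arm the reverse, D = 0.2 would shift the estimate by 0.2 × 2/30 = 0.013, about a fifth of an SE. The extra term would remove that too.

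The reply of harmless conservatism does not extend to the country subgroup, where the error is bias.

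**Conclusion.** The point holds as one of precision for the primary analysis and of bias for the country subgroup analysis. If the countries' trends differ, the primary interval is too wide: about 5–7% at a log-odds difference of 0.2 and 18–27% at 0.4. If they agree, nothing is lost. A reader should not infer that the primary estimate is biased or its test invalid.

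In the treatment-by-country comparison, about 97–99% of any trend difference would appear as effect modification. The facility-size subgroup has the same structure, but size-specific trends were not simulated.

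The sizes rest on assumed trend differences, CAC 0.97, a log-odds variance of 0.6, about 80 births a week and balance within country.

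**What to change.** Before comparative results are seen, amend SAP 25.2.2.2 and 25.2.3 as follows:

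- Add a country-by-period fixed effect to the primary model, to the clinical secondary-outcome models that use both periods, and to the country subgroup model.
- Add facility-size-by-period at least to the facility-size subgroup model.
- Keep the main-effects model as a sensitivity analysis, and as the fallback for rare outcomes whose larger model does not converge.
- Leave the quantitative implementation outcomes (SAP 25.2.3.6) unchanged. They are measured only after the intervention, so a period interaction is undefined there.
- Review the decision not to use a small-sample correction at the same time, because the robust SE becomes slightly smaller.

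The cost is SAP wording and one to three degrees of freedom among 60 facilities. With equal trends, the empirical SE in simulation B rose only from 0.0753 to 0.0757 with country-by-period, and to 0.0766 with both terms. Added after results are known, the same terms would look data-driven.
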